### $\lambda_z$ and AUCinf Criteria

The following criteria will be used to report  $\lambda_z$ :

- At least three quantifiable concentrations will be used in the regression
- $C_{max}$  or data prior to  $C_{max}$  will not be included in the regression.

QMD Ref: Worldwide-TMP-ST-006-4.0 Effective: 12Aug2019	Governing QMD: Worldwide-SOP-ST-001
Confidentiality Statement	

This document is the property of Worldwide Clinical Trials Inc. and may not be duplicated, copied, altered or removed from company without prior approval from Worldwide Quality Assurance or in compliance with Worldwide Standard Operating Procedures.

# Worldwide Clinical Trials Controlled Quality Management Document

- The adjusted regression coefficient ( $R^2_{adj}$ ) should be  $\geq 0.80$ .

If these acceptance criteria are not met,  $\lambda_z$  and descriptive parameters ( $\lambda_z$  time range, Adj R^2, etc.) will be retained in a parameter listing for informational purposes;  $\lambda_z$  will be excluded from summary statistics. Parameters calculated using  $\lambda_z$  (AUCinf, T1/2, CL/F, etc.) will be reported as ND (not determinable).

If  $\lambda_z$  acceptance criteria are met and  $AUC_{inf}$  is estimable, the following criteria are used to report  $AUC_{inf}$ :

- The percentage of  $AUC_{inf}$  based on extrapolation should be  $<30.0\%$ .

If the percentage of  $AUC_{inf}$  based on extrapolation is 30.0% or greater,  $AUC_{inf}$  and  $AUC_{extrap}$  will be excluded from summary statistics, subsequent pharmacokinetic parameter calculations (e.g.  $CL/F$ ,  $V_z/F$ ), and statistical analysis (e.g. ANOVA).

## 6.3 Conventions

All clinical data listings, summaries, figures and statistical analyses will be generated using SAS (Version 9.4 or higher).

Summaries of the clinical data will be presented by treatment and/or overall unless otherwise stated.

PK data listings, summaries, figures, and statistical analyses will be generated using Phoenix™ WinNonlin® (Version 8.1 or higher) or SAS (Version 9.4 or higher). PK concentration data will be summarized by analyte and treatment at each nominal sample time. PK parameter data will be summarized by analyte and treatment.

Treatment labels will be displayed as follows:

## Treatment A

## Treatment B

Footnotes describing each treatment will be provided in each output.

Treatment sequence labels will be displayed as follows:

## Sequence AB

## Sequence BA

Overall

Listings will be sorted in the following order treatment sequence, subject, visit and parameter unless otherwise stated. All data will be listed.

For clinical data, continuous variables will be summarized by the number of non-missing observations, mean (Gmean and Amean), median, standard deviation, and minimum and maximum.

QMD Ref: Worldwide-TMP-ST-006-4.0 Effective: 12Aug2019 | Governing QMD: Worldwide-SOP-ST-001

**Confidentiality Statement**

This document is the property of Worldwide Clinical Trials Inc. and may not be duplicated, copied, altered or removed from company without prior approval from Worldwide Quality Assurance or in compliance with Worldwide Standard Operating Procedures.

Worldwide Clinical Trials Controlled Quality Management Document			
 WORLDWIDE CLINICAL TRIALS	Sponsor:	Opiant Pharmaceuticals	
	Protocol Number:	OPNT003-PK-001	

PK data (concentration-time data and PK parameters) will be summarized by the number of non-missing observations (n), mean, standard deviation (SD), median, minimum (min), maximum (max), and coefficient of variation (CV%), calculated as  $(SD/\text{Mean})*100$ . In addition, the geometric mean and geometric CV%, calculated as  $\text{SQRT}[\exp(\text{SD}^2 \text{ of log transformed data})-1]*100$ , will be reported for  $C_{\max}$  and AUCs.

Categorical variables will be summarized by presenting the frequency and percent. Percentages will be based on the number of non-missing observations or the subject population unless otherwise specified. For each variable, all categories will be shown. Zero frequencies (but not the percent) within a category will be presented.

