## 1 INTRODUCTION

This document details the planned statistical analyses for Opiant Pharmaceuticals, protocol “OPNT003-PK-001” study titled “A Two-Period, Two-Treatment, Randomized Crossover Study of the Pharmacokinetics of Nalmefene by Intranasal and Intramuscular Administration in Healthy Volunteers”.

The proposed analyses are based on the contents of the final version of the protocol (dated 11-NOV-2020) and the protocol clarification letter (dated 04-JAN-2021).

This will be an inpatient, open-label, randomized, 2-period, 2-treatment, 2 sequence, crossover study in healthy volunteers. Each subject will receive 2 treatments during the 2 dosing periods (1 treatment per dosing period):

Treatment A (Test)	3 mg nalmefene hydrochloride IN dose (one 0.1 mL spray of a 30 mg/mL solution in one nostril)
Treatment B (Reference)	1.0 mg nalmefene IM dose (1.0 mL of 1.108 mg/mL nalmefene hydrochloride solution as a single dose in the gluteal muscle)

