AUC 0-30min	Area under the concentration–time curve from time-zero to 30 min; calculated using the linear trapezoidal rule allowing for extrapolation/interpolation to 30min
AUC last (AUC 0-t )	Area under the concentration–time curve from time-zero to the time of the last quantifiable concentration; calculated using the linear trapezoidal rule
AUC last/Dose	AUC last adjusted for the nominal administered dose
AUC inf	Area under the concentration–time curve extrapolated to infinity, calculated as: $AUC_{inf} = AUC_{last} + C_{last}/\lambda_z,$ where $C_{last}$ is the last quantifiable concentration and $\lambda_z$ is the terminal elimination rate constant. The percentage of AUC inf based on extrapolation should be <30.0%
AUC inf/Dose	AUC inf adjusted for the nominal administered dose
AUC% Extrap	The percentage of AUC inf based on extrapolation, calculated as: $\%AUC_{Extrap} = (AUC_{inf} - AUC_{last})/AUC_{inf} * 100$
$\lambda_z$	The observed elimination rate constant ( $\lambda_z$ ); estimated by linear regression in the terminal phase of the log concentration-time profile; see additional criteria below
T 1/2	The observed terminal elimination half-life calculated as: $T_{1/2} = \ln(2)/\lambda_z$
C last	The last quantifiable concentration, determined directly from individual concentration-time data
T last	Time of the last quantifiable concentration
CL/F	Apparent total body clearance after extravascular administration, calculated as: $CL/F = Dose/AUC_{inf}$
Vz/F	Apparent volume of distribution following extravascular administration based on the terminal phase, calculated as: $Vz/F = Dose/(AUC_{inf} * \lambda_z)$
Fre l	Ratio of dose-adjusted AUC inf following IN administration of the test product relative to dose-adjusted AUC inf following IM administration of the reference product

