## 6.11 PK Analyses

Blood samples for determination of plasma concentrations of nalmefene will be collected at:

Predose (0 h), and at 2.5, 5, 7.5, 10, 15, 20, 30, and 45 minutes and 1, 2, 3, 4, 6, 8, 12, 18, 24, 36, and 48 hours post dose.

Concentration-time data will be tabulated by nominal time, analyte, and treatment using descriptive statistics. For presentation of the individual data and summary statistics, concentrations below the limit of quantitation (BLQ) will be set to zero.

Individual subject and mean plasma concentration-time data will be presented graphically on linear and semi-logarithmic scales. Mean data will be plotted using nominal sample times, and individual data will be plotted using actual times.

PK parameters for nalmefene will be calculated as described in section 5.2.13.

PK parameters will be summarized by analyte and treatment using descriptive statistics.

Comparison of the log-transformed PK parameters  $C_{\max}$ ,  $AUC_{0-2.5\text{min}}$ ,  $AUC_{0-5\text{min}}$ ,  $AUC_{0-10\text{min}}$ ,  $AUC_{0-15\text{min}}$ ,  $AUC_{0-20\text{min}}$ , and  $AUC_{0-30\text{min}}$ ,  $AUC_{\text{last}}$ , and  $AUC_{\text{inf}}$  across treatments will be performed using an analysis of variance (ANOVA) model and the two one-sided t-tests procedure at the  $\alpha = 0.05$  level of significance. The model will include sequence, treatment, and period as fixed effects and subject nested within sequence as the random effect. The following comparison(s) will be made:

- Test Product (Treatment A) vs. Reference Product (Treatment B)

The ratios of the geometric means (Test / Reference) and 90% confidence intervals will be reported. The analysis will be performed in SAS using PROC GLM.

Conclusions regarding the results of the statistical analysis (ANOVA) of PK parameters across treatments will be based on the ratio of the geometric means (Test / Reference) and the 90% confidence interval about the ratio. No significant difference will be demonstrated if the 90% confidence intervals are fully contained within the limits of 80.00% to 125.00%.

QMD Ref: Worldwide-TMP-ST-006-4.0 Effective: 12Aug2019	Governing QMD: Worldwide-SOP-ST-001
Confidentiality Statement	

This document is the property of Worldwide Clinical Trials Inc. and may not be duplicated, copied, altered or removed from company without prior approval from Worldwide Quality Assurance or in compliance with Worldwide Standard Operating Procedures.

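### Frel, the SAP's only dose-adjusted IN-versus-IM comparison, is summarised by an arithmetic mean with no geometric mean and no confidence interval, so it will sit above the dose-scaled AUCinf ratio from section 6.11

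*SAP*

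**What the plan says.** Section 6.2.8 of the SAP lists Frel among the PK parameters and defines it as "Ratio of dose-adjusted AUC inf following IN administration of the test product relative to dose-adjusted AUC inf following IM administration of the reference product". The same list contains Cmax/Dose, AUClast/Dose and AUCinf/Dose, each "adjusted for the nominal administered dose". According to section 1, the test is a "3 mg nalmefene hydrochloride IN dose". The reference is 1.0 mg nalmefene IM, given as 1.0 mL of a 1.108 mg/mL hydrochloride solution.

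Section 6.3 (Conventions) gives all PK parameters the same descriptive set: n, arithmetic mean, SD, median, minimum, maximum and CV%. The geometric mean and geometric CV% "will be reported for $C_{\max}$ and AUCs". Frel is neither a Cmax nor an AUC, so it receives neither statistic.

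Section 6.11 opens its inferential part with "Comparison of the log-transformed PK parameters" and names Cmax, six partial AUCs, AUClast and AUCinf. Frel and the dose-normalised parameters are absent. The sentence "The ratios of the geometric means (Test / Reference) and 90% confidence intervals will be reported" therefore does not reach Frel.

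**The concern.** The two doses differ about threefold, so only a dose-adjusted contrast shows how much of the intranasal dose reaches the circulation relative to the intramuscular dose. Frel is the only such contrast planned, because the dose-normalised parameters are summarised by treatment and not compared.

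The rest of the plan works on the log scale. Section 4 sizes the study with log-normal methods, and section 6.11 reports geometric mean ratios with 90% CIs. Frel leaves that framework. An arithmetic mean of ratios is pulled upward by the spread of the ratios, and it is not symmetric. With equal dose-adjusted exposure, the expected mean of IN/IM and the expected mean of IM/IN would both exceed 1.

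The study report could then carry two relative bioavailabilities from the same subjects: mean Frel in Table 14.4.2, and a lower value obtained by dividing the AUCinf ratio in Table 14.4.3 by the dose ratio. The plan does not say which one to cite, and the one labelled Frel would have no interval.

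**Working it through.** **Plan's own figure.** The SAP states no value, variability or precision for Frel or AUCinf. As a check on the log-normal crossover set-up used below, take the AUC0-10/Dose row of section 4 (ISCV 129.21%, GMR 127.06%, N = 60). The non-inferiority margin is not stated and is assumed to be 80%, with one-sided 5% alpha. With SE = σ_w·√(2/N) and N − 2 degrees of freedom, power is 81.1%, as the SAP states.

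**Link between Frel and 6.11.** For one subject,

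Frel = (AUCinf_A/Dose_A) / (AUCinf_B/Dose_B) = (AUCinf_A/AUCinf_B) / (Dose_A/Dose_B).

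The doses are nominal constants, so the geometric version of Frel is the 6.11 AUCinf ratio divided by the dose ratio. Its 90% CI is the 6.11 interval divided by the same number. The dose ratio is 3/1.0 = 3.00 or 3/1.108 = 2.71, depending on the dose basis.

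**Arithmetic against geometric.** Let d be a subject's log ratio, with variance V. For log-normal data the expected arithmetic mean of the ratios is the geometric mean ratio times exp(V/2). With equal within-subject variances and no subject-by-treatment interaction, V = 2σ_w² and σ_w² = ln(1 + ISCV²), so the factor is exp(σ_w²) = 1 + ISCV².

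**Size.** The AUCinf ISCV is an assumed range. The half-width is that of the 90% CI on the log scale for n = 60: 1.672 × σ_w × √(2/60).

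| Assumed ISCV | Factor 1 + ISCV² | Log of factor | 90% CI half-width (log) |
|---|---|---|---|
| 10% | 1.010 | 0.010 | 0.030 |
| 15% | 1.023 | 0.022 | 0.046 |
| 20% | 1.040 | 0.039 | 0.060 |
| 30% | 1.090 | 0.086 | 0.090 |
| 40% | 1.160 | 0.148 | 0.118 |

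Example at 30%: σ_w = √ln(1.09) = 0.294, and 1.672 × 0.294 × √(2/60) = 0.090. The interval would run from 0.914 to 1.094 times the ratio. At 20% it would run from 0.941 to 1.062 times the ratio.

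**Simulation check.** In 20,000 simulated trials of 60 subjects at each ISCV, the arithmetic mean exceeded the geometric mean in every trial. The average factors were 1.010, 1.022, 1.039, 1.088 and 1.157 for the five rows above. The sample median divided by the geometric mean averaged 1.0001 to 1.0014.

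**The case against.** The strongest reply is that nothing important depends on Frel. Section 2 asks whether 3 mg IN gives systemic exposure comparable to 1.0 mg IM, doses as given, and section 6.11 answers that with geometric mean ratios and 90% CIs. Frel is not an endpoint in section 3.1 and has no part in the 80.00% to 125.00% rule. This stands. A reader might infer that the upward bias reaches the primary objective, but the documents do not support that.

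The median of Frel is also planned. For log-normal ratios it targets the same quantity as the geometric mean, so the report would not lack a nearly unbiased summary. With n and SD it would also have some indication of spread. This stands too, but the SAP does not name the median as the estimate and gives it no interval.

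The dose-adjusted ratio and its CI can be had by one division from 6.11, and AUCinf/Dose, as an AUC, would get a geometric mean by treatment. That is correct. It makes the repair nearly free, but leaves the number labelled Frel as the arithmetic mean.

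Finally, bias presupposes a target. The SAP does not say that Frel estimates a geometric mean ratio, or that it is formed per subject. With subject-by-treatment interaction, part of the gap reflects real differences between subjects. This limits how exactly the factor can be stated. It does not remove the mismatch with 6.11, because the arithmetic mean of unequal positive ratios always exceeds their geometric mean.

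**Conclusion.** The point holds as a reporting gap in a supportive, descriptive parameter. Frel has no geometric mean and no confidence interval. Read as a per-subject ratio, its arithmetic mean will lie above the dose-scaled AUCinf ratio of 6.11, by roughly 1% to 16% over an assumed AUCinf ISCV of 10% to 40%. The size rests on log-normality, equal within-subject variances, no subject-by-treatment interaction, and the same subjects in both calculations. It also treats the 6.11 least-squares ratio as the geometric mean of the subject ratios, which is exact when the two sequences are equal in size.

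Two larger effects might be inferred, and neither is supported. The lowest ISCV in section 4 (74.40%, for AUC0-30/Dose) would give 1 + 0.744² = 1.55, an excess of 55%. That ISCV belongs to a partial AUC over the first 30 minutes, and the SAP gives no ground for applying it to AUCinf. Most of the raw difference between Frel and the 6.11 AUCinf ratio is the dose ratio itself (2.71 or 3.00), which is there by design.

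The dose basis is a separate matter. Section 1 describes the reference as 1.0 mg nalmefene from a 1.108 mg/mL hydrochloride solution, while the titles of Tables 14.4.1 to 14.4.3 in section 9 call it 1.0 mg of the hydrochloride. The choice moves Frel by 3.00/2.71, or 10.8%, and these places must be reconciled.

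**What to change.** In section 6.11, state that Frel is reported as the geometric least-squares mean ratio (A/B) of AUCinf/Dose with its 90% CI, from the model already specified. Add it as one row in Table 14.4.3. In section 6.3, add Frel to the parameters given a geometric mean and geometric CV%. State in 6.2.8 that Frel is calculated per subject, and keep the individual values in the listing.

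The cost is a few words in the SAP and one table row, with no new data or model. The reported Frel may be slightly lower than the arithmetic mean would have been.

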### 6.3.1 Decimal Places

Derived data where it is known in advance the result will be an integer for example, day will be presented with zero decimal places.

Means, medians and percentiles will be displayed to one more decimal place than the data, dispersion statistics (e.g. standard deviation) will have two more decimal places, and the minimum and maximum will be displayed to the same number of decimal places as reported in the raw data. Percentages will be displayed with one decimal place.

For PK data, individual concentrations will be reported to 3 significant figures and individual PK parameters will be reported to 3 significant figures. For summary statistics, n will be reported as a whole number; mean, standard deviation, median, minimum, maximum, and geometric mean will be reported to the same precision as for individual data. CV% and geometric CV% will be reported to 3 significant figures; p-values will be reported to 3 significant figures. Percent ratios of the geometric least squares means and associated 90% confidence intervals will be reported to 2 decimal places.

## 6.4 Subject Disposition

Subject disposition will be summarized for all randomized subjects as follows:

- The number of subjects who were randomized and who are in each analysis population will be summarized by treatment sequence and overall.
- The number of early withdrawals and the reasons for withdrawals will be tabulated by treatment sequence and overall.

## 6.5 Protocol Deviations

A listing of protocol deviations will be provided within [Appendix 16.2](#) of the CSR.

QMD Ref: Worldwide-TMP-ST-006-4.0 Effective: 12Aug2019	Governing QMD: Worldwide-SOP-ST-001
Confidentiality Statement	

This document is the property of Worldwide Clinical Trials Inc. and may not be duplicated, copied, altered or removed from company without prior approval from Worldwide Quality Assurance or in compliance with Worldwide Standard Operating Procedures.

Worldwide Clinical Trials Controlled Quality Management Document			
 WORLDWIDE CLINICAL TRIALS	Sponsor:	Opiant Pharmaceuticals	
	Protocol Number:	OPNT003-PK-001	

## 6.6 Baseline Comparability

The comparability of treatment sequences with respect to subject demographics and Baseline characteristics will be assessed in a descriptive manner, but no formal statistical testing will be performed.

Standard continuous or categorical variable summaries will be presented by treatment sequences and overall for the following variables based on the Safety Population.

### 6.6.1 Demographic Data

Standard continuous or categorical variable summaries will be presented by treatment sequence and overall for the following variables based on the Safety Population.

- Age at Informed Consent (years)
- Gender
- Ethnicity
- Race, where more than one race is selected the subject will be presented under the ‘Multiple Races’ category in the summary but each selected race will be identified in the listing.
- Weight at Screening (kg)
- Height at Screening (cm)
- BMI at Screening (kg/m^2)

## 6.7 Medical History

Listings of previous and ongoing conditions at screening will be presented for the Safety Population. Conditions will be coded using the Medical Dictionary of Regulated Activities (MedDRA) version 23.1 or higher.

Prior conditions are defined as all conditions starting and stopping before the date of first dose of study drug. Ongoing conditions are defined as conditions present on or after the date of first dose of study drug.

## 6.8 Substance Use

All substance use data will be listed for the Safety Population.

## 6.9 Prior and Concomitant Medications

Prior and concomitant medications will be listed for the Safety Population.

QMD Ref: Worldwide-TMP-ST-006-4.0 Effective: 12Aug2019	Governing QMD: Worldwide-SOP-ST-001
Confidentiality Statement	
This document is the property of Worldwide Clinical Trials Inc. and may not be duplicated, copied, altered or removed from company without prior approval from Worldwide Quality Assurance or in compliance with Worldwide Standard Operating Procedures.	

Worldwide Clinical Trials Controlled Quality Management Document			
 WORLDWIDE CLINICAL TRIALS	Sponsor:	Opiant Pharmaceuticals	

Prior medications are defined as all medications starting and stopping before the date of first dose of study drug. Concomitant medications are defined as medications taken on or after the date of first dose of study drug.

Medications will be coded using World Health Organization Drug Dictionary (WHODD) Version September 2020.

## 6.10 Exposure to Study Drug

All dosing information will be listed.

## 6.11 PK Analyses

Blood samples for determination of plasma concentrations of nalmefene will be collected at:

Predose (0 h), and at 2.5, 5, 7.5, 10, 15, 20, 30, and 45 minutes and 1, 2, 3, 4, 6, 8, 12, 18, 24, 36, and 48 hours post dose.

Concentration-time data will be tabulated by nominal time, analyte, and treatment using descriptive statistics. For presentation of the individual data and summary statistics, concentrations below the limit of quantitation (BLQ) will be set to zero.

Individual subject and mean plasma concentration-time data will be presented graphically on linear and semi-logarithmic scales. Mean data will be plotted using nominal sample times, and individual data will be plotted using actual times.

PK parameters for nalmefene will be calculated as described in section 5.2.13.

PK parameters will be summarized by analyte and treatment using descriptive statistics.

Comparison of the log-transformed PK parameters  $C_{\max}$ ,  $AUC_{0-2.5\text{min}}$ ,  $AUC_{0-5\text{min}}$ ,  $AUC_{0-10\text{min}}$ ,  $AUC_{0-15\text{min}}$ ,  $AUC_{0-20\text{min}}$ , and  $AUC_{0-30\text{min}}$ ,  $AUC_{\text{last}}$ , and  $AUC_{\text{inf}}$  across treatments will be performed using an analysis of variance (ANOVA) model and the two one-sided t-tests procedure at the  $\alpha = 0.05$  level of significance. The model will include sequence, treatment, and period as fixed effects and subject nested within sequence as the random effect. The following comparison(s) will be made:

- Test Product (Treatment A) vs. Reference Product (Treatment B)

The ratios of the geometric means (Test / Reference) and 90% confidence intervals will be reported. The analysis will be performed in SAS using PROC GLM.

Conclusions regarding the results of the statistical analysis (ANOVA) of PK parameters across treatments will be based on the ratio of the geometric means (Test / Reference) and the 90% confidence interval about the ratio. No significant difference will be demonstrated if the 90% confidence intervals are fully contained within the limits of 80.00% to 125.00%.

QMD Ref: Worldwide-TMP-ST-006-4.0 Effective: 12Aug2019	Governing QMD: Worldwide-SOP-ST-001
Confidentiality Statement	

This document is the property of Worldwide Clinical Trials Inc. and may not be duplicated, copied, altered or removed from company without prior approval from Worldwide Quality Assurance or in compliance with Worldwide Standard Operating Procedures.

Worldwide Clinical Trials Controlled Quality Management Document			
 WORLDWIDE CLINICAL TRIALS	Sponsor:	Opiant Pharmaceuticals	
	Protocol Number:	OPNT003-PK-001	

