## 2 STUDY OBJECTIVES

The primary objective is to

- Determine the pharmacokinetics (PK) of 3mg nalmefene hydrochloride IN compared to a 1.0 mg dose of nalmefene administered IM, to demonstrate systemic exposure comparable to an approved IM dose

The secondary objective is to

- Evaluate the safety and tolerability of IN nalmefene

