## 4 SAMPLE SIZE

This study is designed to obtain information regarding the PK of IN nalnefene under the conditions of this study. The number of subjects has been determined based on the data from the pilot study.

The sample size was based on Geometric Means Ratio (GMR) and Intrasubject Variability (ISCV) results obtained for partial AUC in the pilot study, covering the initial 30 minutes. Sample size calculations are based on the non-inferiority t-test for log-normal distributed data and were performed for study designs: 2x2x2 (2 treatments x 2 sequences x 2 periods), using a target power of 80% and alpha level of 5%.

Parameter	Total ISCV %	GMR %	Sample size estimation	Expected power
AUC 0-5 mins/Dose	178.15	149.40	48	81.0
AUC 0-10 mins/Dose	129.21	127.06	60	81.1
AUC 0-15 mins/Dose	159.69	108.76	168	80.1
AUC 0-20 mins/Dose	127.97	125.68	60	81.0
AUC 0-30 mins/Dose	74.40	123.57	32	81.5

QMD Ref: Worldwide-TMP-ST-006-4.0 Effective: 12Aug2019	Governing QMD: Worldwide-SOP-ST-001
Confidentiality Statement	

This document is the property of Worldwide Clinical Trials Inc. and may not be duplicated, copied, altered or removed from company without prior approval from Worldwide Quality Assurance or in compliance with Worldwide Standard Operating Procedures.

Worldwide Clinical Trials Controlled Quality Management Document			
 WORLDWIDE CLINICAL TRIALS	Sponsor:	Opiant Pharmaceuticals	
	Protocol Number:	OPNT003-PK-001	

Based on these findings a sample size of 60 subjects has been selected. For this study 68 subjects will be enrolled.

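### The sample size in Section 4 powers a non-inferiority test on dose-normalised partial AUCs, but Section 6.11 decides by two-sided 80.00–125.00% equivalence on unadjusted parameters, so the stated power of about 80% does not apply

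*SAP*

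**What the plan says.** **Section 4 (Sample Size).** "Sample size calculations are based on the non-inferiority t-test for log-normal distributed data", for a 2x2x2 crossover with 80% target power and 5% alpha. The table covers AUC0-5, AUC0-10, AUC0-15, AUC0-20 and AUC0-30, each divided by dose. It ends: "Based on these findings a sample size of 60 subjects has been selected", with 68 to be enrolled. No non-inferiority margin is given.

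**Section 6.11 (PK Analyses).** Comparison of Cmax, six partial AUCs, AUClast and AUCinf "across treatments will be performed using an analysis of variance (ANOVA) model and the two one-sided t-tests procedure" at the 0.05 level. None of these parameters is written per dose. Conclusions "will be based on the ratio of the geometric means (Test / Reference) and the 90% confidence interval about the ratio". One criterion follows: "No significant difference will be demonstrated if the 90% confidence intervals are fully contained within the limits of 80.00% to 125.00"%.

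**Section 6.2.8 (PK Parameters)** defines dose-adjusted versions of Cmax, AUClast and AUCinf as separate parameters, and none for the partial AUCs. Section 6.11 compares none of the dose-adjusted versions.

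**Section 2 (Study Objectives).** "Determine the pharmacokinetics (PK) of 3mg nalmefene hydrochloride IN compared to a 1.0 mg dose of nalmefene administered IM", in order "to demonstrate systemic exposure comparable to an approved IM dose".

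**The concern.** A non-inferiority test has only a lower bound, so a test-to-reference ratio well above 100% helps it. A two-sided rule also has an upper bound, so the same ratio counts against it. Three of the five planning ratios in Section 4 (149.40, 127.06 and 125.68%) already exceed the 125.00% limit in Section 6.11. Power for the first test says nothing about power for the second.

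The scale matters too. Dividing by dose moves the ratio and its interval by a constant, but the limits are fixed, so a shift of about 2.7- to 3-fold decides the outcome. The omission of the dose divisor in 6.11 cannot safely be read as shorthand, because 6.2.8 treats dose-adjusted parameters as distinct. For the partial AUCs the missing definition in 6.2.8 is itself only a labelling gap.

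At stake is the reading of the primary objective. If the SAP stays as it is, it does not settle whether the result is judged as non-inferiority or equivalence, or per mg or for the doses as given. That choice could then be made with the data in view.

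**Working it through.** **Inputs.** GMR, within-subject CV (ISCV) and N from the Section 4 table; limits and alpha from Section 6.11; doses from Section 1. Assumed: a non-inferiority margin of 0.80 and one-sided alpha of 5%, because Section 4 states neither the margin nor the sidedness.

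**Formulas.** σ = √ln(1 + CV²); SE = σ√(2/N); df = N − 2. Non-inferiority power is the probability that a noncentral t with noncentrality ln(GMR/0.80)/SE exceeds t(0.95, df). Power of the 6.11 rule (two one-sided tests, TOST) is obtained by integrating over the chi-square distribution of the residual variance.

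**Step 1: reproduce Section 4.** Example, AUC0-10 at N = 60: σ = √ln(1 + 1.2921²) = 0.991; SE = 0.991 × √(2/60) = 0.181; noncentrality = ln(1.2706/0.80)/0.181 = 2.56; t = 1.672; power 81.1%.

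| Per dose | ISCV % | GMR % | N | Stated power % | Recomputed % |
|---|---|---|---|---|---|
| AUC0-5 | 178.15 | 149.40 | 48 | 81.0 | 81.0 |
| AUC0-10 | 129.21 | 127.06 | 60 | 81.1 | 81.1 |
| AUC0-15 | 159.69 | 108.76 | 168 | 80.1 | 80.1 |
| AUC0-20 | 127.97 | 125.68 | 60 | 81.0 | 79.9 |
| AUC0-30 | 74.40 | 123.57 | 32 | 81.5 | 82.0 |

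The table is, as Section 4 says, non-inferiority power. One-sided 2.5% does not fit: it gives about 70 to 72%.

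**Step 2: the 6.11 rule on the dose-normalised scale.** No passage states this version; it is the reading kinder to the SAP. The last column is the factor exp(t × SE) by which the 90% interval extends either side of the ratio at N = 60. An interval centred on 100% fits only if this is below 1.25.

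| | Power %, Section 4 GMR, N=60 | N=68 | Power %, true ratio 100%, N=60 | N=68 | N for 80% at ratio 100% | Half-width factor |
|---|---|---|---|---|---|---|
| AUC0-5 | <0.0001 | <0.0001 | <0.01 | <0.03 | 494 | 1.44 |
| AUC0-10 | 0.0024 | 0.0081 | <0.01 | <0.03 | 340 | 1.35 |
| AUC0-15 | 0.0001 | 0.0002 | <0.01 | <0.03 | 438 | 1.41 |
| AUC0-20 | 0.0031 | 0.0106 | <0.01 | <0.03 | 336 | 1.35 |
| AUC0-30 | 3.4 | 4.5 | 14.7 | 23.3 | 154 | 1.22 |

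For the three parameters whose planning ratio exceeds 125%, power at that ratio cannot exceed 5% at any N. At a true ratio of 100%, 80% power would need an ISCV of about 43% at N = 60 (46% at N = 68), against 74 to 178% planned.

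**Step 3: the 6.11 rule as written, unadjusted.** Unadjusted ratio = per-dose GMR × dose factor. Section 1 gives the test as 3 mg of hydrochloride and the reference as "1.0 mL of 1.108 mg/mL nalmefene hydrochloride solution as a single dose", so the factor is 3/1.108 = 2.71 on the same salt basis. The titles in Section 9 label the reference as 1.0 mg of hydrochloride, which gives 3/1.0 = 3.0. Both are shown because 6.2.8 does not name the form.

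| | Ratio % (factor 2.71) | Ratio % (factor 3.0) | P(whole 90% CI above 125%), factor 2.71, N=60 |
|---|---|---|---|
| AUC0-5 | 405 | 448 | 99.99% |
| AUC0-10 | 344 | 381 | 99.99% |
| AUC0-15 | 294 | 326 | 99.33% |
| AUC0-20 | 340 | 377 | 99.99% |
| AUC0-30 | 335 | 371 | 100.00% |

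With factor 3.0 the smallest such probability is 99.85%. The probability of meeting 80.00–125.00% is below 1e-10 % for every parameter, at N = 60 and at N = 68.

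**Step 4: non-inferiority at the chosen N, margin 0.80 assumed.** Per unit dose: 88, 81, 43, 80 and 97% at N = 60; 92, 85, 47, 84 and 98% at N = 68. For the doses as given: above 99.9% for each.

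**The case against.** Section 4 opens by describing the study as one meant to gather PK information. Section 6.11 bases its conclusions on the ratio and its interval, and the 80.00–125.00% sentence only defines when one particular label applies. Nothing calls it the success criterion, so an interval wholly above 125% could still be reported and interpreted. The protocol and the clarification letter that Section 1 cites may fix hypothesis, margin and scale. The 0.80 margin is inferred and fits imperfectly: at that margin AUC0-20 would need 62 subjects, not the tabled 60. The ratios of 294 to 448% assume that the pilot per-dose ratios carry over to the trial doses, and the SAP does not give the pilot doses. Finally, no estimate or interval would change.

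Much of this stands as a limit on what can be claimed. It cannot be said that the reading will be chosen after the data, only that this SAP does not settle it. The unadjusted figures and the non-inferiority figures are conditional on their assumptions. The conflict itself remains. The objective is to demonstrate comparable exposure, 6.11 offers a single numerical criterion for that, and both conflicting statements are in the SAP, so this is not an omission left to the protocol. The dose-normalised figures in Step 2 need neither the margin nor the carry-over assumption.

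**Conclusion.** The concern holds, and the SAP is wrong as written. The stated power of about 80% belongs to a different hypothesis and a different scale from the rule in Section 6.11. On the kinder, dose-normalised reading, that rule has at most 0.0031% power for four of the five sized AUCs and 3.4% for AUC0-30 at N = 60 (0.011% and 4.5% at N = 68). These figures rest only on Section 4's GMR and ISCV and the 6.11 limits. Unadjusted, power is effectively zero and the whole interval is expected above 125%, provided the per-dose ratios carry over to the trial doses. No power can be computed for Cmax, AUC0-2.5, AUClast or AUCinf, which have no planning values. This must be fixed before database lock, because it concerns the decision rule for the primary objective.

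**What to change.** Bring Sections 4 and 6.11 to one hypothesis, one set of limits and one scale (doses as given, or per mg on the same salt or base form), chosen against the primary objective, and restate the power for the rule kept. The choice is the sponsor's:

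- **Non-inferiority per unit dose (the test that was sized).** State the margin, define partial AUC per dose in 6.2.8, and conclude from the lower limit of the 90% interval. Disclose power at the chosen N, recomputed with the sponsor's own margin. With 0.80 it is about 43% for AUC0-15 at N = 60 and 47% at N = 68.
- **Non-inferiority for the doses as given.** Say so, state the margin, and report power near 100% under the planning values.
- **Two-sided 80.00–125.00%.** Withdraw the power of about 80%, say which scale applies, and give the power from Step 2 or Step 3.

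In every case, replace the wording about no significant difference, which misdescribes an equivalence conclusion, and name the partial AUCs that decide.

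**Cost.** SAP text, plus a protocol amendment if the protocol fixes the rule. No new analysis is needed: at one-sided 5%, the non-inferiority test is the lower limit of the 90% interval already planned, and dose adjustment shifts ratio and interval by a constant. Either non-inferiority route gives up an equivalence claim and any upper limit on exposure. The equivalence route means stating power that is effectively zero unadjusted, or at most 3.4% (N = 60) or 4.5% (N = 68) dose-normalised.
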